4.1 Study Endpoints

4.1.1 Efficacy endpoints

4.1.1.1 Primary Efficacy Endpoint

- Histological evaluation of tissue for selective fat necrosis, with sparing of the dermis and epidermis, following truSculpt treatment vs. untreated bilateral control.

4.1.2 Safety Endpoint

- Incidence and severity of adverse device effects during the study period, including subject pain level during RF treatment.

4.2 Study Duration

Subjects enrolled in this trial will be asked to participate for up to 3 months and will complete 3 visits: 1 screening visit, 1 RF treatment visit, and 1 follow-up visit (biopsy collection visit) on the day of their planned abdominoplasty surgery.

4.3 Study Assessments

4.3.1 Safety Assessments

4.3.1.1 *Incidence and Severity of Adverse Events:*

Following the first RF treatment, adverse device effects (ADEs) will be assessed post-treatment and at each subsequent subject visit using the following scale:

- 1= mild: requires minimal or no treatment and does not interfere with the Subject's daily activities.
- 2= moderate: may cause some interference with functioning.
- 3= severe: interrupts Subject's usual daily activity and may require treatment.

4.3.1.2 *Treatment-related Discomfort*

Subjects will be asked to rate the average amount of discomfort experienced during RF treatment using the Pain Rating Scale found in Appendix 3.

4.4 Study Discontinuation

The study sponsor has the right to terminate this study at any time. Reasons for terminating the study may include, but are not limited to, unsatisfactory subject enrollment or the incidence or severity of adverse events in this study, or other studies with the study device, indicates a potential health hazard to subjects.

4.5 Investigator Selection

Investigators will be invited to participate in the study based on their medical specialty, experience conducting clinical research studies and experience in the use of energy based devices for aesthetic indications. The site's access to potential study subjects and ability to cooperate with study requirements will also be considered.

5 STUDY POPULATION

5.1 Study Subject Recruitment and Selection

Approximately 14 male or female subjects, ages 24 to 60, Fitzpatrick Skin Type I-VI, who are scheduled for abdominoplasty, and will undergo one RF treatment on tissue to be removed during their abdominoplasty, will be studied. Subjects will be recruited to participate from those patients who present themselves to the site requesting abdominoplasty surgery, or from those patients who respond to advertisement. Only subjects who meet all Inclusion and Exclusion Criteria and provide written informed consent will be enrolled into the study.

Each subject will be evaluated by the Investigator to assess his/her suitability for entry into the study according to the following inclusion and exclusion criteria.

5.1.1 Inclusion Criteria

To be included in the study, subjects must meet all of the following Inclusion Criteria:

1.	Male or Female, 24 to 60 years of age (inclusive)
2.	Fitzpatrick Skin Type I – VI (Appendix 3)
3.	Has visible fat bulges or skin laxity in the abdominal region
4.	Scheduled to undergo surgery (abdominoplasty).
5.	Non-smoking for at least 6 months and willing to refrain from smoking for the duration of the study.
6.	Subject must agree to not undergo any other procedure(s) in the abdominal region during the study period.
7.	Subject must be able to read, understand and sign the Informed Consent Form.
8.	Subject must adhere to the follow-up schedule and study instructions.
9.	Subject must adhere to the same diet/ exercise/medication regimen for the entire course of the study.
10.	Willing to provide histology samples during the surgery from the intended to be harvested areas.
11.	Post-menopausal or surgically sterilized, or using a medically acceptable form of birth control at least 3 months prior to enrollment and during the entire course of the study, and no plans to become pregnant.

5.1.2 Exclusion Criteria

Subjects will be excluded from the study if they meet any of the following Exclusion Criteria:

1.	Participation in a clinical trial of another device or drug in the target area during the study period.
2.	Any type of prior cosmetic treatment to the target area within 12 months of study participation e.g., radiofrequency, cryolysis or light-based treatments.
3.	Any prior invasive cosmetic surgery to the target area, such as liposuction.
4.	Has a pacemaker, internal defibrillator, implantable cardioverter-defibrillator, nerve stimulator implant, cochlear implant or any other electronically, magnetically or mechanically activated implant.
5.	Has metal implant(s) within the body, such as surgical clips, plates and screws, intrauterine device (IUD), artificial heart valves or artificial joints.
6.	Significant concurrent illness, such as diabetes mellitus, cardiovascular disease, peripheral vascular disease or pertinent neurological disorders.
7.	Diagnosed or documented immune system disorders.
8.	History of any disease or condition that could impair wound healing.
9.	History of diseases stimulated by heat, such as recurrent herpes zoster in the treatment area, unless treatment is conducted following a prophylactic regimen.
10.	History of keloid formation, hypertrophic scarring or abnormal/delayed wound healing in the treatment area.
11.	Infection, dermatitis, rash or other skin abnormality in the target area.
12.	Currently undergoing systemic chemotherapy or radiation treatment for cancer, or

	history of treatment in the target area within 3 months of study participation.
13.	Pregnant or currently breastfeeding.
14.	As per the Investigator's discretion, any physical or mental condition which might make it unsafe for the subject to participate in this study.

5.2 Subject Numbering

Each enrolled subject will be assigned a subject ID number, comprised of the sequential number assigned for each subject treated and the subject initials. The subject initials will be comprised of the first letter of the first and last name.

5.3 Subject Discontinuation Criteria

If possible, every subject should remain in the study until completion of the required follow-up period. However, participation in this study is completely voluntary and a subject can choose to withdraw from the study at any time. In addition, a subject can be discontinued for any of the following reasons: the Principal Investigator decides that continuing in the study would not be in the subject's best interest, a subject is noncompliant with the protocol, a subject has a serious reaction to the treatment, or the study is stopped. In addition, subjects may be discontinued from the study if s/he develops any of the exclusion criteria during the study period. A subject will be considered lost to follow-up only after three unsuccessful, documented attempts to contact the subject have been made.

6 STUDY PROCEDURES

A summary of all required study procedures and assessments can be found in Appendix 1.

6.1 Screening and Enrollment Visit Procedures

The following screening procedures will be performed:

1. Informed Consent process.
2. Review of subject medical history.
3. Assessment of treatment area.
4. Assessment of concomitant medications.
5. Assign subject to a subgroup.

6.2 RF Treatment Visit

The following procedures will be performed at the RF Treatment Visit:

1. If needed, cleanse subject's treatment area with a mild cleanser to remove any cosmetics, perfume or lotions and then dry the area.
2. Prior to performing RF treatment, the Investigator should confirm the subject continues to meet the study eligibility criteria, including asking about any changes in medical history and/or concomitant medications or significant increase or decrease in subject weight.
3. Using a surgical marker, mark the subject's abdomen as it will be marked on the day of the subsequent planned abdominoplasty procedure.

4. Place the return pad on the subject's upper lateral back. Connect the neutral electrode cable after the return pad has been applied.
5. The subject should be lying down and comfortable while undergoing RF treatment and the operator should have easy access to the treatment area.
6. Conduct RF treatment according to the parameters listed in Table 2 with one imprint applied to the subject's abdomen over the tissue intended to be removed during the following abdominoplasty procedure.

Table 2. TruSculpt RF Device Treatment	
RF Power	[REDACTED]
Pulse Duration	[REDACTED]
Frequency	[REDACTED]
Target Skin Temperature	[REDACTED]
Handpiece Size	[REDACTED]

7. Place the handpiece on the skin of the area to be treated and ensure the electrode is in full contact with the skin at all times. Do not apply excess pressure as this may diminish treatment effects and cause additional subject discomfort. The operator must wear surgical gloves during RF treatment.
8. After the imprint is delivered, an image will be taken of the subject's markings and post-treatment hyperemia pattern showing the location of the imprint. The image will be added to the subject's chart. The pulse duration for the imprint and the target temperature achieved during RF treatment will be recorded in the subject's chart.
9. The subject will be asked to rate the average level of discomfort experienced during and after completion of treatment using the Pain Rating Scale found in Appendix 3.
10. Investigator will assess and record any immediate post-treatment adverse device effects.
11. The "Before and After Treatment Instructions" will be explained and provided to the subject (see Appendix 4).

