Safety Endpoint	Incidence and severity of adverse device effects during the study period, including subject pain level during RF treatment
Subject Population	Female and male subjects, age 24 to 60 years, Fitzpatrick skin type I-VI
Planned Schedule	First subject enrolled: June 2017 Last subject last visit: June 2018

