9.4 Safety Analyses

Device-related and procedure-related adverse effects (AEs) and subjects who prematurely terminate from the study due to an adverse device effect, including the treatment-related pain ratings, will be tabulated and analyzed. For a given AE term, counting will be done by subject, not by event, i.e. for a subject reporting the same AE more than once; the event will be counted only once, at the most severe and longest duration. The number and percentage of subjects experiencing each AE Term will be descriptively summarized. Subject pain ratings during treatment will also be summarized descriptively.

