11.6 Data Collection, Record Keeping and Storage

The principal investigator is responsible for assuring that all study records including case report forms (CRFs), informed consent forms, device accountability records, source documents (e.g., medical records, histology reports etc.) and other study records are complete, accurate and recorded in a timely manner.

CRFs should not be the only record of a patient's participation in the study and will be used for transcribing data from source documents which are the point of first entry of data collected for each subject (with the exception of documents listed under **B**). The investigator or research staff at the site will ensure that:

A. Source documentation thoroughly and adequately documents:

1. That patient is participating in a clinical study and has been properly informed and consented prior to participation in the study,
2. Medical history,
3. Concomitant medications,
4. Patient's condition upon entering and during the course of the study,
5. Any adverse event(s) that might have occurred (in addition to the Visit CRFs and/or Adverse Device Effect CRF and/or Cutera SADE form completed),
6. Results of any diagnostic tests/histology conducted during the study.

B. The following data will be recorded directly onto CRFs:

7. Patient meets study inclusion and exclusion criteria,
8. A record of the treatment parameters, including the date of each RF treatment and any other adjunct therapy, a drawing of the patients abdomen showing the treatment location, and the vial numbers containing control and treatment biopsies,
9. Any protocol deviations,
10. Subject Questionnaire(s),
11. Study related improvement assessments by the investigator or investigator's designee,

12. Treatment-related pain ratings.

C. The following documents will be maintained in the study records:

13. The Investigator or the research staff will check signed informed consent for accuracy and will always keep the original copy of the signed informed consent in the CRF binder.
14. All correspondence with an Institutional Review Board (IRB), the sponsor, or FDA including required reports will also be retained in the study records.
15. Records of receipt, use or disposition of the investigational device.

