Appendix 2: Pain Rating Scale

Subjects will be instructed to rate the pain associated with RF treatment by indicating a number that best represents the overall average pain experienced using the following scale:

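### The step that collects the pain score (6.2 step 9) asks about discomfort during and after treatment, but the safety endpoint, 4.3.1.2 and the last sentence of 9.4 concern pain during RF treatment only

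*Combined protocol and SAP*

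**What the plan says.** The safety endpoint is stated twice. The Protocol Summary gives it as "Incidence and severity of adverse device effects during the study period, including subject pain level during RF treatment", and 4.1.2 repeats the pain element: "including subject pain level during RF treatment". The assessment definition in 4.3.1.2 has the same window: "Subjects will be asked to rate the average amount of discomfort experienced during RF treatment". So does the last sentence of 9.4: "Subject pain ratings during treatment will also be summarized descriptively".

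Section 6.2 step 9, carried out at the RF Treatment Visit, differs. There the subject is to "rate the average level of discomfort experienced during and after completion of treatment".

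Three other places mention the rating without a period:
- The first sentence of 9.4 covers several safety items, "including the treatment-related pain ratings, will be tabulated and analyzed".
- The visible text of Appendix 2 tells subjects to "rate the pain associated with RF treatment by indicating a number that best represents the overall average pain experienced".
- Section 11.6 includes the pain ratings in list B, which opens "The following data will be recorded directly onto CRFs".

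Both 4.3.1.2 and 6.2 step 9 send the reader to Appendix 3 for the pain scale. Appendix 3 is the Fitzpatrick classification; the scale is Appendix 2.

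**The concern.** The endpoint, the assessment definition and the analysis agree with one another, and the instruction that produces the data does not. Site staff work from the visit procedure. Someone who follows step 9 together with the single overall number of Appendix 2 could reasonably record one average covering the treatment and the time after it. Section 9.4 would then report that number as pain during treatment, which it would not be.

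Pain is the one measure named within the safety endpoint, and each subject has one RF treatment, so there is one occasion to collect it. Because 11.6 has the rating written straight onto the CRF, no separate source document is required from which a during-only score could be rebuilt. Discomfort recorded as an adverse device effect is a second record, but it uses a three-level severity grade and is a different measure.

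**Working it through.** The plan gives no figure to reproduce. The check is a comparison of text.

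**Statements of the rating period**

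| Place | Role | Period |
|---|---|---|
| Protocol Summary, safety endpoint | endpoint | during |
| 4.1.2 | endpoint, repeated | during |
| 4.3.1.2 | assessment definition | during |
| 9.4, last sentence | analysis | during |
| 6.2 step 9 | collection | during and after |
| 9.4, first sentence | analysis | none given |
| 11.6, list B | recording | none given |
| Appendix 2, visible text | scale instruction | none given |

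Four statements say during, one says during and after, and three are silent. The first two rows state the same endpoint, so the four come from three distinct sources. The count shows where the mismatch lies; it does not measure its effect.

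**Is the score collected anywhere else?** The Biopsy Collection Visit (6.3) lists no pain rating. Step 9 is the only visible collection step.

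**What each reading of step 9 would yield**

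1. *One average over both periods.* Write D for average pain during treatment, P for average pain afterwards, and w for the weight the subject gives to the treatment period. As a simplification, the recorded score is A = wD + (1 − w)P, so A − D = (1 − w)(P − D). Only A is recorded. Without w and P, D cannot be recovered.
2. *Two ratings.* D and P are both recorded. The last sentence of 9.4 already selects D, so the endpoint is intact.
3. *One question, asked after completion, about pain during treatment.* The record is D, as 4.3.1.2 intends.

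Only reading 1 does harm. The grammar of step 9 favours it, because the phrase about completion is attached to the discomfort experienced and not to the time of asking. The sentence does not exclude the other two.

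**How long can the after period be?** Step 8 delivers the photograph once the imprint is complete, step 9 is the rating, step 10 is the check for immediate adverse device effects and step 11 is the handover of instructions. All belong to one visit. Any after component therefore runs only from the end of the imprint to the question.

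**Size.** Neither w nor P − D is given, and the pulse duration is blacked out, so A − D cannot be computed. Exposure is about 14 subjects × 1 treatment = about 14 scores.

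**The case against.** The strongest reply is that step 9 is loosely worded and simply means that the question is put once treatment is over. Two of the three readings leave the endpoint untouched, and the documents do not show that the harmful one is intended. Appendix 1, the scale itself in Appendix 2 and the CRF are not visible here, and any of them might settle the matter. The CRF bears most directly, since the rating is entered there. All of this stands. It limits the claim to a mismatch in wording that could produce the wrong score; it does not show that the wrong score will be collected. It does not remove the mismatch, because no visible passage reconciles the sections.

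The stakes are also low. Section 9.3.1 plans no hypothesis test, and neither a stopping rule nor the histology endpoint uses the score. Table 3 gives the expected duration of pain as the procedure itself, which suggests little later pain to blend in. Later discomfort is picked up separately as an adverse device effect, with severity and duration (6.3 step 3).

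Two stronger readings should be resisted:
- A reader might infer from Appendix 4, which warns of tenderness for up to a week, that days of later discomfort could enter the score. They cannot: the score is taken at the treatment visit.
- A reader might infer that 9.4 leaves open which rating is summarized. Its first sentence gives no period, but its last sentence names the during-treatment rating.

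**Conclusion.** The point holds as an inconsistency in data collection. Step 9 asks about a wider period than the endpoint it serves. Read literally as one average, it yields a score that is not the stated endpoint and from which the endpoint cannot be recovered.

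The effect is probably small. That judgement rests on the order of the steps in 6.2, which confines the after part to the interval before the question at the same visit. It is not a calculated figure, and no direction is claimed. The consequence is limited to the descriptive pain summary in about 14 subjects. It gives no reason to doubt the rest of the safety tabulation or the primary endpoint.

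The mismatch in the text is certain. Whether the collected data would miss the endpoint depends on which reading the site adopts and on pages not visible here. The two wrong appendix pointers are certain and clerical. The point is worth acting on because correcting one sentence removes the doubt.

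**What to change.** - Reword 6.2 step 9 to match 4.3.1.2: the question is asked after completion and concerns average discomfort during the RF treatment.
- If post-treatment discomfort is also wanted, record it as a separate rating and report it separately.
- Check that Appendix 1, the Appendix 2 scale and the CRF use the same window, and edit them only if they do not.
- Correct the pointers in 4.3.1.2 and 6.2 step 9 from Appendix 3 to Appendix 2.

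Section 9.4 needs no change for the during-treatment rating. The cost is one reworded sentence, two corrected pointers and a check of three items. An extra CRF field is needed only if the separate post-treatment rating is wanted.

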4 STUDY DESIGN

This is a single-center, prospective, non-randomized, open-labeled study in approximately 14 subjects, age 24 to 60 years, who are scheduled for abdominoplasty, and will undergo one RF treatment in the abdominal region. Subjects will receive 1 RF treatment with the truSculpt device [REDACTED]

[REDACTED]

One treatment will be performed by the truSculpt device on one abdominal subarea, while the other abdominal subarea will not be treated and will serve as a control. Subjects will have incisional or full-thickness punch skin biopsies. Biopsies will be harvested from tissue to be removed during the abdominoplasty, and will subsequently be cultured. At least two biopsy samples for each subject will be obtained during the abdominoplasty: at least one from the treatment area and at least one from the control area. The purpose of the biopsies is to examine and compare potential histological changes in cutaneous and sub-cutaneous tissue levels that occur as a result of RF treatment.

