Appendix 3: Fitzpatrick Skin Type Classification

Appendix 4: Before and After Treatment Instructions

Before Treatment Instructions:

- The day before and the day of your truSculpt treatment, drink plenty of water to ensure you are well hydrated. The truSculpt treatment works best when patients have had plenty of fluids prior to treatment.

After Treatment Care Instructions:

- Redness is expected and should resolve within a few hours.
- Mild swelling may occur and should go away within 72 hours.
- Tenderness of the treatment area may persist up to 1 week.
- Avoid hot showers or baths and avoid scrubbing the treated area when bathing.
- Please call your study doctor if you experience any of the following in your treatment area:
 - Blistering
 - Bleeding
 - Burn
 - Crusting or scabbing
 - Pain or Tenderness, Redness or Swelling that lasts more than 72 hours
 - Nodules or lumps
- Do not pop or un-roof blisters if they occur.
- If you need to take any over-the-counter medications for discomfort after the RF treatment, take non-aspirin pain medications, such as Tylenol or Advil.

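### In the readable text, the pre-treatment instructions are handed over only at the end of the single RF treatment visit, too late for their day-before element

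*Combined protocol and SAP*

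**What the plan says.** Section 4 fixes the exposure: "Subjects will receive 1 RF treatment with the truSculpt device". Section 4.2 sets out the visits: each subject "will complete 3 visits: 1 screening visit, 1 RF treatment visit, and 1 follow-up visit (biopsy collection visit" on the day of surgery.

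Section 6.1 opens with "The following screening procedures will be performed" and lists five items: consent, medical history, assessment of the treatment area, concomitant medications and subgroup assignment. None is the handing over of an instruction sheet.

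In section 6.2 the treatment is step 6 ("Conduct RF treatment according to the parameters listed in Table 2"). The post-imprint image is step 8, the discomfort rating step 9, and step 10 reads "Investigator will assess and record any immediate post-treatment adverse device effects". Step 11, the last, is where the combined sheet "will be explained and provided to the subject (see Appendix 4". Section 6.3 does not mention the sheet.

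Appendix 4 has a single pre-treatment item: "The day before and the day of your truSculpt treatment, drink plenty of water to ensure you are well hydrated". The reason follows at once: "The truSculpt treatment works best when patients have had plenty of fluids prior to treatment".

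**The concern.** An instruction about the day before treatment is useful only if it arrives before that day. The one step in the readable text that delivers it comes after the imprint has been applied, and no second treatment follows to which it could apply. The step as written therefore defeats the purpose of half of the sheet.

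The stake is modest but real. The study is meant to evaluate device performance, and its own leaflet links preparation to performance. If preparation is left to chance, subjects may differ on a condition that the protocol considers relevant, and nothing on the page records who had prepared. The check at 6.2 step 2 covers eligibility, medical history, medications and weight change, but not preparation.

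The untreated contralateral control helps only in part. Anything that hydration does equally to both sides drops out of the comparison. If hydration changes the response to RF, as the leaflet's sentence implies, the within-subject comparison does not remove that, because only one side is treated.

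**Working it through.** There is no figure to reproduce and no formula to apply. The plan states no error rate, power or effect size, and section 9.3.1 provides for descriptive summary only. The check is one of timing. Call the treatment day day 0.

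| Element | Source | Timing |
|---|---|---|
| Hydration, first part | Appendix 4 | day −1 |
| Hydration, second part | Appendix 4 | day 0, useful only before the imprint |
| RF treatment | 6.2 step 6 | day 0 |
| Image, discomfort rating, adverse effect check | 6.2 steps 8 to 10 | day 0, after the imprint |
| Sheet explained and handed over | 6.2 step 11 | day 0, listed last |
| Any later RF treatment | sections 4 and 4.2 | none |

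1. **Day −1 part.** The only readable handover is on day 0. The day-before element is missed wherever step 11 falls within that visit, so this conclusion does not depend on the order of the list.
2. **Day 0 part.** This does depend on the order. The list is not strictly chronological, since handpiece placement (step 7) comes after the instruction to conduct the treatment (step 6). Steps 8 to 10 are all post-treatment, however, so a site reading down the list would reach step 11 after treatment.
3. **A later occasion.** There is one RF treatment visit and one imprint, so the sheet cannot serve a subsequent session.
4. **An earlier occasion.** Neither the five items in 6.1 nor any other readable step supplies the sheet before day 0. Two places cannot be checked: the Appendix 1 schedule, which section 6 describes as the summary of all required procedures and which is a figure not shown, and the consent pages, which were removed.

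Within the readable text, then, the before part arrives late for every subject treated according to the listed steps, out of approximately 14 planned. That counts how many subjects the written order covers. It does not measure any effect on the endpoint.

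**The case against.** The strongest reply is that absence from 6.1 proves little. Those five items are not a full account of what happens before treatment: they omit the check of inclusion and exclusion criteria, which section 5.1 requires and which 6.2 step 2 treats as already done. The consent discussion in section 11.2 covers the procedure and the study requirements, and inclusion criterion 8 expects subjects to follow study instructions. The sheet, or its content, could be conveyed at that stage, or be scheduled in Appendix 1. This stands. It is why the conclusion is conditional and confidence is moderate. It does not remove the mismatch, because the one step that names the sheet still places it after treatment.

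Two stronger readings are tempting, and the documents support neither.

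- **A reader might infer that no subject can follow the instruction.** Drinking water does not depend on receiving a leaflet. Subjects may be well hydrated anyway or be told informally, and Appendix 1 and the consent material cannot be seen. What the text supports is that the written procedures do not deliver the instruction in time.
- **A reader might infer that a weak or patchy histological response would be uninterpretable.** The leaflet gives no size for a hydration effect, hydration is not a condition of eligibility or treatment, and no hypothesis test depends on it. Section 6.2 step 8 also records pulse duration and the temperature achieved for each imprint, which gives some subject-level information on how treatment was delivered. An unrecorded condition is not a demonstrated bias.

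It is also fair to say that adding a line to 6.1 would not by itself guarantee day-before notice, because the documents give no minimum interval between screening and the RF visit. The fix allows for this.

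**Conclusion.** The point holds as a sequencing inconsistency between section 6.2 and Appendix 4. In the readable text the before part of the sheet is provided only at the last step of the only RF treatment visit, so under the written procedures a subject would not have it in time for its day-before element. This rests on two assumptions: that neither Appendix 1 nor the consent material supplies it earlier, and that the site follows the listed steps. If Appendix 1 does supply it earlier, the remaining task is to align 6.1 and 6.2 with it.

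The effect on the histology endpoint is unknown, and none is claimed. Severity is minor and confidence moderate. The case for acting is that the correction costs almost nothing, and that a late handover cannot be put right for a subject who has already been treated.

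**What to change.** Reconcile sections 6.1 and 6.2 with Appendices 1 and 4 on when each part of the sheet is given:

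- Provide and explain the before part ahead of the RF treatment visit, early enough for its day-before element. Screening would serve if it takes place at least one day earlier. If the two visits can fall closer together, the text needs to say how the sheet reaches the subject in time.
- Keep the after-care part at 6.2 step 11.
- Optionally, add a yes/no record at 6.2 step 2 of whether the before part was followed. The sheet defines no amount and no analysis of such an item is planned, so it would be a rough self-report for description only.

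No change to the clinical content of the sheet is proposed. The cost is one added line at screening, plus one case report form item if the optional record is adopted. No extra visit or procedure is needed, provided screening is at least a day before treatment.
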